9.2 NUMBER OF SUBJECTS, DURATION OF FOLLOW-UP AND STUDY DURATION

A total of 145 subjects will be enrolled in the study. Assuming a 40% screen failure rate, approximately 245 subjects will be enrolled and screened to obtain 145 enrolled and treated subjects. All subjects will be followed for 12 months.

It is anticipated that enrollment in the study will take approximately 12 months. Including the 12-month follow-up period, the study is expected to last 24 months.

9.3 INFORMED CONSENT AND POINT OF ENROLLMENT

The IRB-approved informed consent will be presented and explained to each prospective subject by the investigator or a trained clinical professional. Once the subject has had ample time to read the consent form, has been informed of all aspects of the study, and has had an opportunity to ask questions, the subject will be given a choice to voluntarily confirm his or her participation in the study as documented by completion of the Informed Consent. After signing the Informed Consent and the HIPAA (Health Insurance Portability and Accountability Act) authorization, the subject can then proceed with the screening visit. The subject has the right to withdraw from the study at any time without consequences, as indicated in the Informed Consent Document.

The subject's signed and dated informed consent must be obtained before conducting any procedure specifically for the study. Subjects are enrolled upon signing the ICD even if they subsequently fail to meet the eligibility criteria.

The principal investigator(s) must retain the original, signed written Informed Consent Document. A copy of the written Informed Consent Document must be given to the subject.

9.4 SCREENING VISIT

After obtaining an understanding of the purpose of this study, then reviewing and signing the Informed Consent Document, all potential subjects will undergo an initial screening examination in order to determine their eligibility for the study. Exams and tests listed in the Screening column of Table 1 should be performed. Refer to Appendix A for instructions for performing the exams.

If both eyes meet the applicable inclusion and exclusion criteria, the eye with higher IOP is recommended to be included in the study. In case of both eyes with same IOP at screening, investigator will select the study eye. The other eye will be excluded based on the first eye already being included in the study.

Once the study eye is identified, subjects will undergo the washout procedure described in Section 9.5 before the Baseline visit.

Note: If a subject does not meet the inclusion/exclusion criteria, he/she may be re-screened after 30 calendar days. Subject should be exited from the study and assigned another subject identification on second screening.

Exam data collected on subjects prior to enrollment as part of the routine clinical practice may serve as Screening data as long as it was collected within 15 days prior to the visit. The only exceptions to this are:

- IOP and IOP-lowering medications. These data must be collected at the Screening visit.
- Visual field: Visual Fields conducted per the protocol method (Humphrey 24-2 SITA standard) within 90 days of the Baseline visit may serve as the Baseline exam.

9.5 WASHOUT OF HYPOTENSIVE MEDICATIONS

Subjects who meet all screening eligibility criteria will be instructed to discontinue their ocular hypotensive medication regimen in the study eye only, and to return for a Baseline visit after completing the appropriate washout period. Glaucoma medication discontinuation can be staged (for patients on multiple medications) so that the pressure increase duration is minimized to the greatest possible extent during the washout period. For example, if a patient is on a prostaglandin (PGA) and a Carbonic Anhydrase Inhibitor (CAI), the PGA could be discontinued 4 weeks prior to the Baseline visit but the allowed to continue until 5 days before Baseline.

If the study subject fails to remember to not use ocular hypotensive medication for the study eye per the required washout period, they can be re instructed to washout and return for the Baseline or 12-month washout IOP visit as long as it falls within the specified visit window.

The minimum wash-out periods are specified in Table 2 below. Note: The maximum washout period is 6 weeks. Therefore, if the study procedure cannot be scheduled within one week of the end of the washout period, the subject should be restarted on glaucoma medication until the Day 0 visit (but after the washed-out diurnal IOP has been obtained).

Table 2: Ocular Hypotensive Medication Washout Periods

Brand Name/Chemical Name	Minimum washout period
Carbonic Anhydrase Inhibitors	
Diamox® (Acetazolamide) – oral Rx	5 days
Neptazane® (Methazolamide) – oral Rx	5 days
Azopt® (Brinzolamide)	5 days
Trusopt® (Dorzolamide Hydrochloride)	5 days
Muscarinic Agonists	
Salagen, Pilocar (Pilocarpine)	5 days
Alpha Adrenergic Agonist	
Alphagan® (Brimonidine)	14 days
Iopidine® (Apraclonidine Hydrochloride)	14 days
Beta Blockers	
Betagan® (Levobunolol Hydrochloride)	28 days
Betoptic® (Betaxolol Hydrochloride)	28 days
OptiPranolol® (Metipranolol)	28 days
Timoptic/Betimol® (Timolol Maleate)	28 days
Prostaglandin Analogs	
Lumigan® (Bimatoprost)	28 days
Travatan® (Travoprost)	28 days
Xalatan® (Latanoprost)	28 days
Zioptan® (Tafluprost)	28 days
Vyzulta® (Latanoprostene Bunod)	28 days
Rho Kinase Inhibitor	
Rhopressa® (Netarsudil)	28 days
Combined Medications	
Combigan® (Brimonidine Tartrate/Timolol Maleate)	28 days
Cosopt® (Dorzolamide Hydrochloride/ Timolol Maleate)	28 days
Simbrinza® (Brinzolamide/Brimonidine Tartrate)	28 days
Other	Contact Sponsor

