9 STUDY PROCEDURES

9.1 STUDY SCHEDULE

Table 1: Study Visit Schedule

Note: The fellow eye should be followed per the PI's usual practice based on the ocular health of the fellow eye.

PROCEDURE	SCREENING (DAY -45 TO -6)	BASELINE (DAY -7 TO 0)	SURGERY (DAY 0)	1 DAY (DAY 1)	1 Wk (DAY 5-9)	1 M (DAY 21-35)	3 M (DAY 70-98)	6 M (DAY 150-210)	12 M (DAY 330-420)	12 M WASHOUT ²⁹ (DAY 330-420)
Informed Consent	X									
Demographics	X									
Medical & Ocular History	X	X								
Medication Log	X	X	X	X	X	X	X	X	X	X
BCVA (ETDRS), with manifest refraction	X	X			X	X	X	X	X	
Visual Field (Humphrey 24-2 SITA)	X									X
IOP (Goldmann)	X			X	X	X	X	X	X ³⁰	
Unmedicated diurnal IOP (Goldmann)		X							X ³¹	X
Slit Lamp Exam	X	X		X	X	X	X	X	X	
Gonioscopy	X				X	X	X	X	X	
Dilated Fundus Exam/C:D Ratio	X								X	
Eligibility Assessment	X	X								
Cataract Extraction + ab-interno transluminal viscoelastic delivery and trabeculotomy			X							
AE Assessment	X	X	X	X	X	X	X	X	X	X

²⁹ The 12 month washout visit is only required for subjects who are taking hypotensive medications at the 12 month visit.

³⁰ This is only required for subjects who are taking hypotensive medications at the 12 month visit.

³¹ If subject is not on any hypotensive medications, a diurnal IOP measurement should be obtained at the 12 month visit as unmedicated IOP.

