9.9 MANAGEMENT OF IOP AFTER SURGERY

This protocol recommends that no IOP-lowering medications should be administered to subjects after the surgery (0 meds on postop day 1) unless medically warranted. Investigators should use their clinical judgement in determining when and why IOP-lowering medications should be reintroduced and if a subject requires surgical re-intervention to manage IOP.

Re-introduction of hypotensive medications should follow the guidelines below:

- The same medication class(es) as used preoperatively should be re-introduced. Dependent on preoperative IOP medication use, the reintroduction/addition of IOP medications postoperatively should follow the order below:
 1. Prostaglandin Analogues
 2. Alpha Agonists
 3. Beta Blockers
 4. Rho Kinase Inhibitor
 5. Carbonic Anhydrase Inhibitors (CAIs)
- No more than one ocular hypotensive agent should be added at a single visit or within a 2-week period.

³² 180° trabeculotomy should be attempted in every eye enrolled in the study. There is a possibility that 180° trabeculotomy may not be possible in each case.

In the event of a steroid response (IOP increase), the usual guidelines requiring a reproducible increase in IOP should be followed; however, topical hypotensive medications should be discontinued once the topical steroid has been discontinued.

If a pressure rise is observed, a paracentesis may be performed as necessary. If a paracentesis is performed and there is no protocol-defined adverse event, the paracentesis will be documented in the subject's medical record, the applicable visit CRF and the Ocular Procedures log. If, however, the paracentesis is performed in conjunction with an AE, then the AE is recorded as such, and the paracentesis is also recorded on the AE CRF as a treatment for the protocol-defined AE (as well as the other CRFs mentioned above).

Medications which have been re-started by the investigator may be discontinued if the investigator's judgment is that the target intraocular pressure has been reached and the continued use of some or all of the therapy may not be required. Discontinuation of medications after re-introduction is recommended to be in the reverse order of re-introduction. The rationale for discontinuation will also be documented on the follow-up form by the investigator.

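### Table 2 requires 28 days of washout for Simbrinza although its two components are listed at 5 and 14 days, with no reason given

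*Combined protocol and SAP*

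**What the plan says.** Table 2 in Section 9.5 lists minimum washout periods by drug class, with a separate block for combined medications. The rows that matter here are:

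- the two components, "Azopt® (Brinzolamide) 5 days" and "Alphagan® (Brimonidine) 14 days";
- their fixed combination, "Simbrinza® (Brinzolamide/Brimonidine Tartrate) 28 days";
- for comparison, "Combigan® (Brimonidine Tartrate/Timolol Maleate) 28 days", and Cosopt (dorzolamide with timolol), also at 28 days. Timolol alone is listed at 28 days and dorzolamide alone at 5.

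The section caps washout at 6 weeks. It also lets sites stage the stopping of several drugs so that the eye spends as little time as possible at raised pressure. Its example is a prostaglandin with a carbonic anhydrase inhibitor: "the PGA could be discontinued 4 weeks prior to the Baseline visit but the allowed to continue until 5 days before Baseline".

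Table 1 (Section 9.1) sets the window "SCREENING (DAY -45 TO -6") for screening, Day -7 to 0 for Baseline, and Day 330 to 420 for both the 12-month visit and the 12-month washout visit. On the latter it adds: "The 12 month washout visit is only required for subjects who are taking hypotensive medications at the 12 month visit". Section 9.9 advises on restarting drops after surgery: "No more than one ocular hypotensive agent should be added at a single visit or within a 2-week period".

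**The concern.** The same two drugs carry two different minimum washouts depending on whether they come in one bottle or two. Elsewhere the protocol treats a combination product as the sum of its parts: the footnote to inclusion criterion 4 and Appendix A, Section 20.10 both count each component as a separate medication. Table 2 departs from that for Simbrinza alone, without saying why.

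What is at stake is time off treatment in an eye with glaucoma, which Section 9.5 itself wants kept short, and a tighter fit in the visit windows. The analysis is not at stake. Washing out for longer than necessary does not make the unmedicated IOP invalid, and no hypothesis, significance level or sample size depends on this row.

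**Working it through.** **Inputs** (Table 2, minimum days): brinzolamide 5, dorzolamide 5, brimonidine 14, timolol 28, prostaglandin analogs 28; Combigan, Cosopt and Simbrinza 28 each. Windows are from Table 1.

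**1. Can the combination rows be reproduced from their components?** When all components stop together, the eye has met every component's minimum once the longest one has passed, so the natural figure is the maximum.

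| Product | Components (days) | Longest | Listed | Difference |
|---|---|---|---|---|
| Combigan | 14, 28 | 28 | 28 | 0 |
| Cosopt | 5, 28 | 28 | 28 | 0 |
| Simbrinza | 5, 14 | 14 | 28 | 14 |

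Two of the three rows are reproduced and Simbrinza is not. Adding its components does not give the listed value either: 5 + 14 = 19.

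**2. Overall washout for an eye.**

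- Simbrinza and no 28-day drug: 28 days as written. Brinzolamide and brimonidine in separate bottles: max(5, 14) = 14 days. Difference: 28 - 14 = 14 days.
- Simbrinza plus a prostaglandin, beta blocker or netarsudil: 28 days either way. Difference: 0.

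**3. Days with no drops at all, if the site stages.** This is the shortest stopping lead among the eye's bottles. For a prostaglandin plus Simbrinza it is min(28, 28) = 28 as written and min(28, 14) = 14 with the row at 14. Overall washout is unchanged, but as written staging gives this eye no relief.

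**4. Fit before Baseline.** The screening window, Day -45 to -6, contains 40 days. Washout starts at screening at the earliest, so the screening day can be no later than the Baseline day minus the washout.

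| Baseline | Washout 28 days | Washout 14 days |
|---|---|---|
| Day 0 | Day -45 to -28: 18 days | Day -45 to -14: 32 days |
| Day -7 | Day -45 to -35: 11 days | Day -45 to -21: 25 days |

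The 28 days fit, and lie within the 6-week (42-day) maximum, but with less room. That also leaves less room to repeat a washout, which Section 9.5 allows only inside the visit window.

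**5. Month 12.** To finish by Day 420, a Simbrinza washout must start by 420 - 28 = Day 392, against 420 - 14 = Day 406. This is a corner case: only eyes on medication at that visit wash out, and the advice in Section 9.9 to add agents singly makes a restart on a two-drug bottle unlikely.

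**The case against.** The strongest reply is that nothing in Table 2 is contradicted. The figures are minimums, a 28-day washout satisfies the 5-day and 14-day rows as well, and a site can comply with all of them. The longest-component rule is not written anywhere. Every block in the table carries one uniform value, so Simbrinza may simply follow a blanket 28 days for combined medications. Eyes on a prostaglandin, beta blocker or netarsudil already face the same 28 days and the same scheduling limits, and exclusion criterion 6 removes eyes for which washout is a significant risk. Staging is optional, and the group carrying the full 14-day burden is narrow and uncounted.

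Most of this stands, and it limits the point. The documents do not show that the cell is a mistake, and a uniform value for combinations is a possible reading. It does not remove the inconsistency. On that reading too, the plan keeps an eye off treatment 14 days longer than its own table accepts for the same two drugs, against the stated aim of staging. For eyes on a prostaglandin or beta blocker, the 28 days follow from the drug itself; for Simbrinza alone, no listed component requires them.

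It can also be said that a mid-study change would apply different minimums within one study. Table 2 already does so by drug, at 5, 14 or 28 days, so a 14-day Simbrinza row adds nothing of a new kind.

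**Conclusion.** The concern holds as a minor, unexplained inconsistency. Simbrinza is the only combination row that does not equal its longest component. The cost is 14 avoidable days off treatment before Baseline for a study eye on Simbrinza and no 28-day drug and, where a site stages, up to 14 further drop-free days for an eye on Simbrinza with a 28-day drug. Scheduling room shrinks as shown above. No effectiveness or safety analysis changes.

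This rests on two assumptions: that the component rows of Table 2 are adequate as they stand, and that washout begins no earlier than the screening visit. The documents do not say how many eyes are on Simbrinza, so the total effect cannot be sized.

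**What to change.** Change the Simbrinza row of Table 2 to 14 days and add a footnote: *The minimum washout of a combination product is that of its component with the longest minimum washout.* Combigan and Cosopt stay at 28 days under this rule. If the sponsor means to keep 28 days for Simbrinza, one sentence giving the reason should be added.

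The cost is one table cell and one footnote in an amendment, with sponsor approval and IRB review as necessary under Section 14. Eyes already washed out for 28 days meet the 14-day minimum, so nothing has to be repeated, and no analysis is altered.

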9.6 BASELINE VISIT

During the Baseline visit, the exams and tests listed in the Baseline column of Table 1 should be performed. Refer to Appendix A for instructions for performing the exams.

9.7 SURGICAL PROCEDURE

During the surgical procedure, cataract extraction should be performed following the surgeon's standard practice. Then, 360° ab-interno transluminal cohesive viscoelastic

delivery followed by 180° trabeculotomy³² using the OMNI Surgical System should be performed only in eyes with uneventful cataract extraction. Eyes with complications related to cataract extraction or IOL implantation should be exited from the study. The region where the trabeculotomy procedure is performed (e.g. superior hemisphere) shall be recorded on the case report forms.

Surgeons should follow their standard peri-operative medication regimen. All the medications should be administered in the form of ocular drops. Any other means of medication administration such as intracameral or intravitreal routes should be avoided.

9.8 FOLLOW-UP VISITS

Follow-up visits should be performed according to the schedule provided in Table 1 (page 17). All attempts should be made to conduct each follow-up visit within the time interval specified in Table 1. Evaluations conducted outside the prescribed time period will be considered protocol deviations.

9.9 MANAGEMENT OF IOP AFTER SURGERY

This protocol recommends that no IOP-lowering medications should be administered to subjects after the surgery (0 meds on postop day 1) unless medically warranted. Investigators should use their clinical judgement in determining when and why IOP-lowering medications should be reintroduced and if a subject requires surgical re-intervention to manage IOP.

Re-introduction of hypotensive medications should follow the guidelines below:

- The same medication class(es) as used preoperatively should be re-introduced. Dependent on preoperative IOP medication use, the reintroduction/addition of IOP medications postoperatively should follow the order below:
 1. Prostaglandin Analogues
 2. Alpha Agonists
 3. Beta Blockers
 4. Rho Kinase Inhibitor
 5. Carbonic Anhydrase Inhibitors (CAIs)
- No more than one ocular hypotensive agent should be added at a single visit or within a 2-week period.

³² 180° trabeculotomy should be attempted in every eye enrolled in the study. There is a possibility that 180° trabeculotomy may not be possible in each case.

In the event of a steroid response (IOP increase), the usual guidelines requiring a reproducible increase in IOP should be followed; however, topical hypotensive medications should be discontinued once the topical steroid has been discontinued.

If a pressure rise is observed, a paracentesis may be performed as necessary. If a paracentesis is performed and there is no protocol-defined adverse event, the paracentesis will be documented in the subject's medical record, the applicable visit CRF and the Ocular Procedures log. If, however, the paracentesis is performed in conjunction with an AE, then the AE is recorded as such, and the paracentesis is also recorded on the AE CRF as a treatment for the protocol-defined AE (as well as the other CRFs mentioned above).

Medications which have been re-started by the investigator may be discontinued if the investigator's judgment is that the target intraocular pressure has been reached and the continued use of some or all of the therapy may not be required. Discontinuation of medications after re-introduction is recommended to be in the reverse order of re-introduction. The rationale for discontinuation will also be documented on the follow-up form by the investigator.

A record of all ocular hypotensive medications added, discontinued or changed will be documented on the appropriate Case Report Form for each scheduled visit or on a Case Report Form for an Unscheduled Visit, if necessary.

Another potential reason for intervention is hypotony. Intervention should only be considered if the hypotony has caused or is likely to cause sequelae such as a flat chamber. No intervention is indicated when the vision is unchanged from screening, there is no persistent choroidal detachment, the anterior chamber is not flat with lens corneal touch, or the patient is asymptomatic. No intervention should be undertaken for hypotony which is not causing, or threatening to cause, a reduction in vision.

Secondary IOP-Lowering Interventions to Control IOP

If the subject requires another glaucoma procedure to control their IOP, the subject should continue to be followed according to standard of care until the adverse event resolves or 1 month post-re-intervention, whichever is longer. Following this, the subject should be withdrawn from the study.

Subjects who have a secondary IOP-lowering intervention will be considered treatment failures for the purpose of the secondary endpoint analyses. These subjects will be included in the Safety Endpoint analyses through their withdrawal from the study.

9.10 WITHDRAWAL AND DISCONTINUATION

All subjects have the right to withdraw at any point during the treatment without prejudice. The investigator can discontinue any subject at any time if continued participation in the study would result in harm to the subject. All efforts should be made by the investigator to retain the subject in the study. If a subject withdraws prematurely from the study, a genuine effort must be made to determine the reason(s) the subject discontinued the study. The reason must be recorded in the subject's file and on the Study Exit Form.

If a subject withdraws from the study post-baseline but prior to surgery, then that subject may be replaced in the study by a newly enrolled subject.

9.11 SUBJECTS LOST TO FOLLOW-UP

Subjects who do not show up for a follow-up must be contacted to attempt to have them come for the follow-up. For those subjects who cannot be reached, at least 3 phone call attempts should be made and documented. If still no response, a registered letter shall be sent to the address on file for the subject in an attempt to make contact. If a subject misses two consecutive follow-up visits without any contact with the study staff, the subject will be considered lost-to-follow-up unless there is a further communication by the subject.

10 ADVERSE EVENTS (AEs)

Adverse Events are defined below. Adverse events that occur in the eye during the trial, whether they are considered to be device related or not, must be documented in the subject's records. Date of the event, its severity, treatment (if any) and the assessed relationship of the event to the study device will be recorded on the Adverse Event Form. Conditions which exist at the time the subject is enrolled do not need to be recorded as adverse events unless they increase in severity during the study.

10.1 DEFINITIONS OF AE, SAE, SADE, USADE

Adverse Event	Any untoward medical occurrence in a subject who has been treated with the device that does not necessarily have causal relationship with the treatment.
Adverse Device Effect	Any unfavorable and unintended sign (including an abnormal laboratory finding), symptom, or disease that is possibly related to the study device.
Serious Adverse Event (SAE)	Any untoward medical occurrence that: 
• Results in death

	
 • Is life-threatening • Requires in-patient hospitalization or prolongs existing hospitalization • Necessitates medical or surgical intervention to preclude permanent impairment of a body function or permanent damage to a body structure • Sight threatening
Unanticipated Adverse Device Effect	Any serious adverse effect on health or safety, any life-threatening problem or death caused by, or associated with a device if that effect, problem, or death was not previously identified in nature, severity, or degree of incidence in the clinical investigational plan; or any other serious problem associated with a device that relates to the rights, safety, or welfare of subjects (21 CFR 812.3(s)). Any sight-threatening event, whether listed in the protocol or not, is considered to be reportable as a UADE

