7.2 SAFETY ENDPOINTS

Safety will be assessed by evaluating the following measures over time:

- Rates of ocular adverse events (intraoperative, postoperative)
- Reduction in best corrected visual acuity (BCVA) from baseline (note: reduction in BCVA due to PCO will not be treated as a safety event)

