10.2 LIST OF ANTICIPATED POTENTIAL ADVERSE EVENTS

Anticipated potential adverse events listed below include those that might reasonably be expected to occur in this study because they are associated with glaucoma, cataract surgery, ab-interno transluminal viscoelastic delivery, trabeculotomy, and/or the risk analysis for OMNI System. Adverse events may occur intra-operatively or post-operatively.

- Layered Hyphema $\geq 1\text{mm}$ (Microhyphema or Hyphema $<1\text{mm}$ is expected and will not be considered an AE)
- IOP increase $\geq 10\text{ mmHg}$ above baseline IOP at ≥ 1 month visit³³
- IOP increase requiring management with systemic medication at ≥ 1 month visit³²
- Need for secondary surgical intervention to manage IOP³²
- Hypotony (IOP $<6\text{ mmHg}$)³⁴ with at least one of the following conditions:
 - Flat anterior chamber requiring anterior chamber reformation
 - Corneal folds
 - Choroidal effusions requiring or undergoing surgical drainage
 - Suprachoroidal hemorrhage

³³ To avoid double counting an event, events of IOP $\geq 10\text{ mmHg}$ above baseline IOP at ≥ 1 month visit that require management with systemic medication or secondary surgical intervention should be reported as “IOP increase requiring management with systemic medication at ≥ 1 month visit” or “Need for secondary surgery intervention to manage IOP,” respectively.

³⁴ Hypotony is defined as “early” if it occurs within 2 weeks of surgery and “late” if it occurs more than 2 weeks after surgery

e) Maculopathy

- Corneal injury
- Corneal edema after 1 week
- Corneal abrasion
- BCVA loss of ≥ 10 letters (ETDRS) at or after 3 months postoperative
- Descemet's membrane tear or detachment
- Chronic anterior uveitis (inflammation of grade 1+ or worse persisting for more than 3 months post-operatively or that recurs less than three months after discontinuing treatment)
- Wound leak
- IOL dislocation and/or damage
- Intracorneal Hematoma
- Posterior capsular tear
- Pupillary block
- Cyclodialysis
- Iridodialysis or significant iris damage
- Peripheral Anterior Synechiae > 1 clock hour
- Suture abscess or other local infection
- Flat or shallow anterior chamber requiring anterior chamber reformation
- Aqueous misdirection
- Choroidal detachment
- Choroidal effusion requiring surgical drainage
- Choroidal hemorrhage
- Suprachoroidal hemorrhage
- Vitreous hemorrhage
- Perforation of sclera
- Clinically significant cystoid macular edema
- Retinal detachment
- Retinal tear

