11.2 ANALYSIS POPULATIONS

The intent-to-treat (ITT) analysis population includes all subjects who are enrolled and treated, regardless of whether or not they have a protocol deviation. Due to the eligibility revision in May of 2019 on requiring at least one ocular hypotensive medication, the modified ITT (mITT) population includes all ITT except for the treated eyes that were not on any ocular hypotensive medication at the screening visit. The per-protocol analysis population (PP) is a subset of mITT, which includes all subjects who have taken at least one ocular hypotensive medication at screening and have uneventful cataract extraction followed by ab-interno transluminal viscoelastic delivery and trabeculotomy, 12 month IOP and medication data, and have no clinically significant protocol deviations. It should be noted that the mITT subjects with an uneventful study procedure but with SSIs before the 12-month visit will be included in the PP population even if they do not have the 12-month IOP and medication data. The primary analyses on the primary and secondary endpoint analyses will be carried out on the per-protocol population.

The safety data will be summarized based on the ITT population. The primary and secondary endpoint analyses will also be performed on the mITT population.

The data will be listed separately for the enrolled subjects that are not treated with OMNI and treated subjects that do not have ocular hypotensive medications at the screening.

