11.5 SAFETY ANALYSIS

All safety analyses will be performed on the ITT population based on all available data.

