11.5.1 ADVERSE EVENT

Adverse events (AEs) will be classified as intraoperative or postoperative. The number and the percent of eyes reporting at least 1 adverse event of a given type will be summarized. Additionally, the number of reports of each type of AEs will be provided.

For each AE, the number and the percent of eyes reported with the event will be summarized by the severity level. For eyes with multiple reports of the same type of AE, the maximum severity will be used. Similarly, the AE relationship to the procedure will be summarized. For eyes with multiple reports of the same type of AE, the closest relationship to the procedure will be used.

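### Adverse events during the preoperative medication washout have no place in the planned adverse event rates, because the definition in Section 10.1 conflicts with Table 1 and the opening of Section 10

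*Combined protocol and SAP*

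**What the plan says.** The Combined protocol and SAP deals with this in several places.

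- **Definition.** Section 10.1 limits an adverse event to "Any untoward medical occurrence in a subject who has been treated with the device". The serious adverse event row beside it has no such limit.
- **Timing.** Section 10.2 states that "Adverse events may occur intra-operatively or post-operatively". The safety endpoint in Section 7.2 names the same two periods, and Section 11.5.1 says "Adverse events (AEs) will be classified as intraoperative or postoperative".
- **Population.** Section 11.5 says "All safety analyses will be performed on the ITT population based on all available data". Section 11.2 defines that population: "The intent-to-treat (ITT) analysis population includes all subjects who are enrolled and treated". It adds that data for enrolled subjects not treated with OMNI will be listed separately.
- **Enrolment and washout.** Section 9.3 puts enrolment at consent: "Subjects are enrolled upon signing the ICD even if they subsequently fail to meet the eligibility criteria". Under Section 9.5, those who pass screening "will be instructed to discontinue their ocular hypotensive medication regimen in the study eye only", for at most 6 weeks, before the Baseline visit.
- **Collection.** Table 1 marks adverse event assessment at every visit, including Screening and Baseline. The opening of Section 10 requires ocular events during the trial to be documented whether or not they relate to the device. It exempts only conditions already present at enrolment that do not worsen.

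**The concern.** Washout is something the study asks for, and the plan treats it as a risk. Exclusion 6 removes subjects whom the investigator judges to be at significant risk from it, and Section 9.5 allows staged discontinuation to shorten the period of raised pressure. A reader would expect the safety results to say how often it did harm.

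Under the 10.1 wording, an event in a subject who never receives the device is not an adverse event at all. Two sites could follow the document in good faith and act differently: one would record a pressure-related event found at Baseline because Table 1 asks for the assessment, and the other would not because 10.1 excludes it. Even if every site records such events, 11.5.1 has no class for them.

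The gap is also selective. Inclusion 5 requires an unmedicated Baseline pressure of 21 to 36 mmHg, so an eye that rises above 36 mmHg after washout fails at Baseline and never joins the safety population. The eyes with the highest washed-out pressures are therefore among those missing from the summaries.

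**Working it through.** **1. The provisions side by side**

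| Situation | Adverse event under 10.1? | Assessed or documented? | In the planned rates? |
|---|---|---|---|
| Washout event, subject later treated | Open to reading: 10.1 names a kind of subject, not a time window | Yes (Table 1, Section 10) | In the safety population, but in neither class of 11.5.1 |
| Washout event, subject never treated | No | Yes by Table 1; under Section 10 only if 10.1 does not govern | No; data listed separately (11.2) |
| Event in the 12-month washout | Yes | Yes | Yes, as postoperative |
| Serious event in an untreated subject | Meets the serious event row, which has no treated-subject limit | Reportable (10.3) | No; data listed separately (11.2) |

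The first two rows are the problem.

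**2. Who can fall in the second row**

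Three routes lead out of the study after washout but before device treatment: failing inclusion 5 at Baseline, withdrawing after Baseline and before surgery (Section 9.10, replacement allowed), and being exited for a cataract-surgery complication before OMNI is used (Section 9.7).

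**3. How many**

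Inputs from Section 9.2: 145 treated, 40% screen failure, about 245 consented.

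- Check of the plan's figure: 145 / (1 − 0.40) = 241.7, rounded up to 242. The stated figure of about 245 is consistent with this.
- Untreated: 245 − 145 = 100, and 100 / 245 = 40.8%. With 242 it is 97, or 40.1%.

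This is an upper bound on untreated subjects who started washout. Those who fail at Screening never stop their drops, and the documents do not divide failures between Screening and Baseline.

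**4. Could events occur in that group?**

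The only safety calculation in the plan is in Section 11.1.3: with 130 eyes, a 95% probability of seeing at least one event whose rate is about 2.4%. Check: 1 − (1 − 0.024)^130 = 0.957. The rate that gives exactly 95% is 1 − 0.05^(1/130) = 2.28%. The plan's figure is reproduced.

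The documents give no washout event rate. As an illustration only, take k untreated subjects who started washout and a rate p. Expected events are k × p, and the probability of at least one is 1 − (1 − p)^k. Both k and p are assumptions; 2.4% is borrowed from Section 11.1.3.

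| k | p = 1% | p = 2.4% | p = 5% |
|---|---|---|---|
| 25 | 0.25 events; 0.222 | 0.6 events; 0.455 | 1.25 events; 0.723 |
| 50 | 0.5 events; 0.395 | 1.2 events; 0.703 | 2.5 events; 0.923 |
| 100 | 1.0 events; 0.634 | 2.4 events; 0.912 | 5.0 events; 0.994 |

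If k is close to zero, so is the loss.

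**5. What the corrected summary could show**

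The denominator would be everyone who started washout. Section 11.1.3 says some treated eyes had no hypotensive medication at screening, so the treated contribution is somewhat below 145. Assume a denominator between 130 (taking the 15 added eyes, 145 − 130, as the unmedicated ones) and 245. The rate detectable with 95% probability, 1 − 0.05^(1/n), is 2.28% at n = 130, 2.04% at n = 145 and 1.22% at n = 245. No sample size changes.

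**The case against.** The best defence is that the plan already captures these events. Table 1 assesses them, Section 10 counts from enrolment, and enrolment is at consent. Section 11.2 lists data for untreated subjects, and Section 9.10 records the reason for any early withdrawal. Estimating washout risk is neither an objective nor a safety endpoint, and giving rates for treated eyes is a reasonable choice in a post-market device study.

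Much of this stands, and it rules out several stronger readings.

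- A reader might infer that washout harms are left out of the safety results altogether. They are not: they can be recorded, and data for untreated subjects are listed. What is missing is a class and a rate.
- A reader might infer that the one-working-day serious event rule does not reach untreated subjects. The serious event row in 10.1 stands alone without the treated-subject condition, and Section 10.3 applies the rule to any ocular serious event.
- A reader might infer that every participant is washed out, or that all of the roughly 100 untreated subjects were. Section 9.5 limits the instruction to those who pass screening, and some treated eyes had no medication to stop.
- A reader might extend the point to the 12-month washout. Those events occur in treated subjects after surgery and fit the postoperative class.

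The defence does not remove the conflict. Section 10 opens by referring to the definitions that follow, so its documentation duty can be read as carrying the 10.1 limit. A listing gives no rate and no denominator. It also does not help treated subjects, whose washout events belong to neither class.

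**Conclusion.** The point holds as an internal conflict with a limited consequence. Section 10.1 disagrees with Table 1 and the opening of Section 10 on whether an untreated subject can have an adverse event. Section 11.5.1 and the safety population then leave preoperative washout events out of every planned rate, for treated and untreated subjects alike.

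The size is bounded rather than known: between none and about 100 of about 245 consented subjects are untreated and started washout, and most of the treated subjects have a preoperative washout with no class for its events. The bound rests on the plan's assumed 40% screen failure rate. The event counts above are illustrations, not predictions. Effectiveness analyses, sample size and serious event reporting are unaffected.

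**What to change.** 1. In Section 10.1, define an adverse event from informed consent onward, so that it agrees with Table 1 and the opening of Section 10. Align the timing statements in Sections 7.2 and 10.2.
2. In Section 11.5.1, add a preoperative (washout) class.
3. Report that class as a count, denominator and percentage for all subjects who started washout, treated or not, separately from the intraoperative and postoperative rates on the ITT population. Section 9.4 gives re-screened subjects a new number, so state whether the denominator counts people or washouts.
4. Keep the listing in Section 11.2 as supporting detail.

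The cost is wording changes and one small table. The Screening and Baseline assessments are already scheduled, so no visit, clinical rule or sample size changes. The start of washout must be identifiable for each subject; the medication log at Screening and Baseline should supply it.
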